Date	27.11.2019		Distribution Informatique pdf
Auteur	BGA		
Contrôle	EBO		
Libération	RAQ		

SYMBIOS Device	ORIGIN®
N of FU visits:	4
Follow-up visits:	Preop / Surgery / 1y / 2y Follow-up visits
Study start date:	DEC 2020
Date first visit first patient:	JAN 2021
Study Scoring:	
Forgotten Joint score (FJS)
 
KOOS Score
 
OKS Score
 
EQ-5D-5L Score
 
A self-administrated patient satisfaction questionnaire (3 questions)

Inclusion criteria:	
Symbios plans to include consecutive eligible subjects which will be treated either with the ORIGIN SYSTEM versus VANGUARD PS.
 
Subjects will be enrolled upon evaluation via a clinical examination at the preoperative stage. Subjects should meet the following criteria:
 
 
• Male and female over 18 years of age
 
• Each patient, or his or her guardian or legal representative, is willing to give informed consent.
 
• Clinically indicated for a total Knee replacement
 
• Females who are not pregnant or lactating and not planning to become pregnant ≤ 12 months. A pregnancy test may be performed to confirm this.
 
• Geographically stable and willing to return to the implanting site for all follow-up visits at 1 year and 2 years.
 

Exclusion criteria:	
Patients meeting any one of the following criteria will be excluded from participating in this study:
 
 
• Life expectancy ≤ 1 year
 
• Age ≥ 80 years
 
• Acute or chronic, local or systemic infection
 
• Mental illness
 
• Muscular, ligamentous, neurological, psychological or vascular deficits
 
• Bone destruction or poor bone quality likely to affect implant stability (requiring a femoral and/or a tibial stem and/or a thick insert)
 
• Any concomitant condition likely to affect implant integration or function
 
• Allergy or hypersensitivity to any of the materials used
 
• For devices in CoCrMo (ISO 5832/4): renal and hepatic impairment
 
• Hip Knee Ankle (HKA) angle < 165° or > 195°
 

SYMBIOS		 symbios  Clinical Investigation Plan	F029.03
Date	27.11.2019		Distribution Informatique pdf
Auteur	BGA		
Contrôle	EBO		
Libération	RAQ		

SYMBIOS Device	ORIGIN®

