### B. Clinical endpoints

#### a) *Primary endpoints*

- The hypothesis regarding the scoring is that patients receiving ORIGIN implants will experience a more natural feel of the prosthesis during the first year after the surgery compared to patients receiving VANGUARD implants (as measured with FJS)
- The primary endpoint of this study is:

SYMBIOS		 symbios  Clinical Investigation Plan	F029.03
Date	27.11.2019		Distribution Informatique pdf
Auteur	BGA		
Contrôle	EBO		
Libération	RAQ		

- To compare the ability of patients to forget their operated knee at 1 year after the surgery, measured by the Forgotten Joint Score 12 (FJS-12 Knee).
- To compare patient satisfaction regarding the surgery with a CE marked custom-made implant (ORIGIN®) versus off-the-shelf (VANGUARD PS) device. A short self-reported questionnaire will be used.

*b) Secondary endpoints will evaluate clinical performance and safety of ORIGIN System:*

- **Secondary endpoints:**

- Evaluate the success of the procedure
- Evaluate surgeon satisfaction regarding the use of implants and instruments
- Evaluate outcomes: complications & revision rate with the ORIGIN SYSTEM at the last (2y) follow-up visit
- To compare the PROMs between the two groups at 1y follow-up and 2y follow-up visits.
- Evaluate performance of the ORIGIN System vs VANGUARD PS at 2 years follow-up: clinical examination and scoring.
- To evaluate/compare the clinical, functional and quality of life outcomes using the following four scores:
  - Clinical examination
  - The Knee Injury and Osteoarthritis Outcome Score (KOOS)
  - The Oxford Knee Score (OKS)
  - The EQ-5D-5L Score
  - A self-administrated patient satisfaction questionnaire.
- To evaluate/compare the clinical, functional and quality of life outcomes with the following surgeon reported scores:
  - The Knee Society Score (KSS) (Objective Knee Indicators only)
  - Knee Society Radiographic Evaluation and Scoring System (KSRESS)
  - The Single Leg Stance Test (SLS)
  - The Timed Up & Go test (TUG)
- Radiological evaluation:
  - X-rays: AP, lateral, sunrise, long leg weight bearing film
  - Femoral patellar arthrosis: Iwano classification (stage 1 mild to 4 very severe),
  - KRESS Radiological assessment: Patellar tilt angle, patellar displacement, tibial slope, anatomical axis (angles  $\alpha - \beta$ ), mechanical axis, (HKA angle, F angle, T angle, HKS angle)

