### c) Follow-up data at 1-year visit

There is an established visit window defined in this study, the following postoperative follow-up data will be collected at 12M (1 year).

The follow-up window is flexible and is set as a guidance to +/-1M for the first visit at 1 year.

The following data will be collected in the eCRF:

- Date of visit (DD/MM/YYYY)
- Name of Surgeon
- Physical examination
  - Weight, (between 20 and 250Kg)
  - Height, (between 80 and 250cm)
  - BMI (kg/m^2)
- Radiological examination per standard of care (ap, lateral, sunrise)-
- Femoral patellar arthrosis (applicable if it is an anatomic patella not a prosthetic implant), patellar tilt angle, patellar displacement, tibial slope, femoral component flexion, anatomical axis ( $\alpha$  angle,  $\beta$  angle), mechanical axis (HKA angle, F angle, T angle, HKS angle)

SYMBIOS		 symbios  Clinical Investigation Plan	F029.03
Date	27.11.2019		Distribution Informatique pdf
Auteur	BGA		
Contrôle	EBO		
Libération	RAQ		

- Surgeon reported scores will be collected during this visit:
  - The Knee Society Score (KSS) (Objective Knee Indicators only)
  - Knee Society Radiographic Evaluation and Scoring System (KSRESS)
  - Single Leg Stance Test or (SLS)
  - Timed up and go (TUG)
- Evaluate radiographic loosening (according to the “Modern Knee Society Radiographic Evaluation System and Methodology for Total Knee Arthroplasty” version 2015)
- Radiolucent lines; Femur, frontal Tibia frontal, Tibia profil, Patella
- Satisfaction of the patient based on performance evaluation of the evaluated device ORIGIN vs VANGUARD based on scoring via FJS questionnaire:
  - FJS score
  - A self-administrated patient satisfaction questionnaire. (3 questions)

The hypothesis regarding the scoring is that patients receiving ORIGIN implants will experience a more natural feel of the prosthesis during the first year after the surgery compared to patients receiving VANGUARD implants (as measured with FJS).

The overall patient satisfaction is expected to be improved after 1-year follow-up for ORIGIN vs VANGUARD.

FJS score at the postoperative visits will be collected per standard of care at the investigational site.

- Evaluate performance of the ORIGIN System vs VANGUARD PS at 1-year follow-up: clinical examination, and scoring. To evaluate/compare the clinical, functional and quality of life outcomes with the following scores:

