### e) Scores

Cf. Forgotten Joint score (FJS) – Chapter XXI. APPENDICES. E. PATIENT SELF-QUESTIONNAIRE

The Forgotten Joint Score (FJS) is a joint-specific questionnaire developed in 2012 (Behrend et al. 2012) with the aim to measure PRO of joint disorders (Hamilton et al. 2017). FJS is designed to measure the ability of the patient to “forget” about their problematic joint after treatment. FJS is available in 3 versions: hip, knee, and shoulder. In the following editorial: *The Forgotten Joint Score Don't Compare Apples to Oranges,* “The Forgotten Joint Score asks the simple question, “Are you aware of the joint that had surgery?” Essentially, does the patient have any sense that there has been surgery on the limb or joint? Although it has been validated as a reliable testing technique in specific surgical procedures, it has not been validated as a method of comparing 2 dissimilar surgical procedures.” This is why this score will only be used to compare patient satisfaction while undergoing a surgery with ORIGIN or with VANGUARD systems.

FJS is defined in 12 questions:

- Functional outcome, pain, stability and daily living ...but additional
- Activity and Sport

The outcome Score is between 0-4. Zero is best outcome. Low score means high satisfaction. All responses are summed and multiplied by 25 (Total= 0-100)

Overall patient satisfaction will therefore be calculated based on patients PROMs. (Patient reported outcome measures) This score will be used to evaluate patient satisfaction with ORIGIN vs VANGUARD which should lead to a higher score (>13.4 points)

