#### *d) Performance outcomes*

The device success will be evaluated via the performance assessment via the overall surgeon and patient satisfaction. Post-operative surgeon overall satisfaction will be assessed via the following answers: very

 <https://www.ncbi.nlm.nih.gov/pubmed/12719681>

Interpretation of changes in health-related quality of life: the remarkable universality of half a standard deviation

SYMBIOS		 symbios  Clinical Investigation Plan	F029.03
Date	27.11.2019		Distribution Informatique pdf
Auteur	BGA		
Contrôle	EBO		
Libération	RAQ		

satisfied, satisfied, and not satisfied. Post-operative patient satisfaction will be assessed via the FJS, with a marked improvement in the natural feel of the prosthesis during the first year after the surgery, and slightly significant improvement at the following interval of 2 years.

A final report will be prepared when all patients have completed their follow-up evaluation. No interim analysis is planned.

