### e) *Statistical Methods and Analysis*

All analyses will be described in a Statistical Analysis Plan (SAP) which will be completed prior to analysis. No interim analysis is planned.

Any deviations from this section and/or the Statistical Analysis Plan will be described and justified in the Final Clinical Study Report, as appropriate.

No statistical techniques will be used to impute missing data for continuous or categorical outcomes. If a subject's data are missing for any reason, that subject will not be included in that portion of the analysis. The number of subjects included in each analysis will be reported so that the reader can assess the potential impact of missing data.

Additional (annual) reports providing only descriptive statistics will only be written upon request of the EC/IRB and/or Regulatory Authority, as applicable.

For statistical analysis, patient satisfaction results will be analyzed into the knee awareness as:

- Never
- Almost never
- Seldom
- Sometimes
- Mostly

The subjects that required further procedures or surgeries on their knee in the initial six months were excluded from this analysis. These patients were excluded from analysis because the outcome and satisfaction scores were likely to be highly influenced by the early additional procedure, and the study was not powered to evaluate the revision rates associated with two implants.

Statistical differences could be identified in:

- Baseline demographics between ORIGIN vs VANGUARD in patient satisfaction, including slightly differences in age, comorbidities and sex.
- Surgeon overall satisfaction regarding both implants ORIGIN and VANGUARD and possible surgical factors who could play a role in the patient outcome or on the performance of the implant?
- Demonstrate superiority of ORIGIN over VANGUARD: higher score by 13.4 points based on MCID evaluation of PROMs.
- If a modular stem is used it could impact radiological analysis: radiolucencies for instance and tibial loosening

SYMBIOS		 symbios  Clinical Investigation Plan	F029.03
Date	27.11.2019		Distribution Informatique pdf
Auteur	BGA		
Contrôle	EBO		
Libération	RAQ		

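### The plan contradicts itself on whether patient satisfaction means the questionnaire or the FJS, and its five-label analysis rule is the output of neither

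*Combined protocol and SAP*

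**What the plan says.** The CIP defines satisfaction in two ways and then gives an analysis rule.

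- **By questionnaire.** VI.B a) lists the FJS-12 comparison at 1 year and, as a separate item, a comparison of satisfaction for which "A short self-reported questionnaire" will be used. The Synopsis endpoint text also ties satisfaction to a self-administered questionnaire. The Synopsis scoring list and the 1-year visit (VIII.F c) give it three questions and list it apart from the FJS.
- **By FJS.** VIII.F e) says of the FJS: "This score will be used to evaluate patient satisfaction with ORIGIN vs VANGUARD which should lead to a higher score (>13.4 points"). X.d says: "Post-operative patient satisfaction will be assessed via the FJS", and makes this part of device success. VI.C and X.b state the satisfaction target as 13.4 points, which X.b derives from the FJS standard deviation.
- **By both.** The 1-year and 2-year visit lists (VIII.F c and d) describe satisfaction as scored through the FJS, then place both instruments under that item.
- **Analysis rule.** X.e: "For statistical analysis, patient satisfaction results will be analyzed into the knee awareness as" five labels, Never to Mostly. The same section also looks for an ORIGIN score higher by 13.4 points.

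Section X contains no scoring or analysis rule for the questionnaire.

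**The concern.** Patient satisfaction is the stated primary objective in the Synopsis and a component of device success in X.d. An analyst who follows Section X would report joint awareness under the name of satisfaction. An analyst who follows VI.B would report the questionnaire.

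The two can tell different stories. In the sponsor's own earlier cohort (IV.B), the mean 1-year FJS is 60.5/100, while 96% of patients are reported, as a separate result, to be satisfied or very satisfied. The instrument behind the 96% is not stated. The trial is unblinded (VII.C), so the choice of definition should not be left open until analysis.

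The five-label rule also departs from the scale used for sizing. Both the sample size and the 13.4-point superiority statement need a point score.

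**Working it through.** **1. Reproduce the plan's sample size.** Inputs: difference 13.4 and SD 26.8 (X.b); z values 1.96 and 0.84 and the two-mean formula (X.a).

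- ES = 13.4/26.8 = 0.5
- n = (2/0.5²) × (1.96 + 0.84)² = 8 × 7.84 = 62.72, so 63 per group
- 10% loss: 63/0.9 = 70 per group
- Power at 63 per group: 0.5 × √(63/2) = 2.806; 2.806 − 1.96 = 0.846; Φ(0.846) = 80.1%. With all 70 evaluable it is 84.1%.

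The figures reproduce, as a comparison of mean FJS points on the 0-100 scale.

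**2. Can the five labels be derived?** VIII.F e) gives the FJS 12 questions with answers coded 0-4. Five labels match five answer levels, so they are probably the answer options of a single FJS item. That is an inference, since no section says so. No section says how 12 answers, or three satisfaction questions, become one label. The rule therefore cannot be carried out on either instrument as written.

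**3. Size of one label step.** Five levels spread over 0-100 give steps of 25 points, and 13.4/25 = 0.54 of a step. Cut into five equal bands of 20 points, 13.4/20 = 0.67 of a step.

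**4. Power if FJS totals were classed (assumption).** As a hand check, rounding to the nearest step adds a variance of 1/12 in step units:

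- SD = √[(26.8/25)² + 1/12] = √(1.149 + 0.083) = 1.110
- ES = 0.536/1.110 = 0.483
- Power = Φ(0.483 × √31.5 − 1.96) = 77.3%

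Simulation used 3,000 trials per scenario and 63 per arm. Scores were normal with SD 26.8 and a difference of 13.4, with and without clipping to 0-100. Assumed control means were 43.3, 47.1 and 60.5, and labels were cut by rounding to 25-point steps or in 20-point bands.

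| Analysis | Power |
|---|---|
| t-test on the 0-100 score | 0.79-0.80 |
| Five classes, order kept (Mann-Whitney, or t-test on 0-4 codes) | 0.73-0.77 |
| Five classes, unordered chi-square | 0.49-0.54 |

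Against the planned 0.80, the loss is about 3-7 percentage points if order is kept and about 26-31 if it is not. X.e names no test, so the documents do not settle which applies.

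**The case against.** Four stronger readings are tempting, and the documents stop short of each.

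- **That the FJS is the wrong instrument for satisfaction.** This follows only if the questionnaire in VI.B governs. VI.C, VIII.F e), X.b and X.d all tie satisfaction to the FJS, and the visit lists put both instruments under it. What is established is an unreconciled contradiction.
- **That the questionnaire is never analysed.** VI.B lists it among the outcomes to be compared, and the Synopsis (collected data) says the reported scores will be compared between arms at each follow-up. What is missing is a scoring and analysis rule in Section X.
- **That five labels are too coarse to detect 13.4 points.** The 0.54 of a step concerns one patient's label, whereas 13.4 is a difference between group means. An ordered analysis keeps about 0.75 power. A split at the median would give about 61%, but no section proposes one.
- **That the primary endpoint is lost.** The Synopsis and VI.B still define it as the FJS-12 at 1 year, and X.e keeps a 13.4-point score comparison. The labels could be read as a descriptive display.

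It is also fair to say that X.e defers to a separate SAP, to be completed before analysis, which is not among the documents. That does not remove the problem. X.e requires deviations from its own text to be described and justified, so an SAP that corrected this would depart from the CIP.

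**Conclusion.** The concern holds as an internal contradiction. Satisfaction is defined by the questionnaire in some sections and by the FJS in others, and the five-label rule in X.e produces the result of neither. It does not match the mean FJS difference on which the trial is sized, or the 13.4-point statement in the same section. It should be corrected before analysis.

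The contradiction rests on the text alone. The size of any power loss does not: about 73-77% with ordered classes and 49-54% with unordered ones depend on assumed cut-points, control means and normal scores, and on the labels being applied to FJS totals at all. The main consequence is ambiguity over what the satisfaction result, and the patient part of device success, will mean.

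**What to change.** In X.e, replace the five-label rule with text such as:

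> The FJS-12 is analysed as the 0-100 joint-awareness score, comparing arm means at 1 year (primary) and 2 years. Satisfaction is analysed separately from the self-administered satisfaction questionnaire on its own response scale, by arm, at 1 and 2 years. The five awareness answers are shown per FJS item, descriptively only.

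Name the test for each comparison and state how the questionnaire is scored. In X.d, take patient satisfaction from the questionnaire and report the FJS as joint awareness. Reconcile VI.C, VIII.F c), d) and e), and X.b in the same edit, so that 13.4 points is stated as an FJS difference and not a satisfaction difference.

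Two scoring statements in VIII.F e) need attention at the same time:

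- "All responses are summed and multiplied by 25 (Total= 0-100") does not give 0-100 if the 12 items are summed, because 12 × 4 × 25 = 1,200. The item mean must be intended.
- "The outcome Score is between 0-4. Zero is best outcome. Low score means high satisfaction" conflicts with a target expressed as a higher score.

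The cost is wording in the CIP and SAP. Both instruments are already collected, so no new data or visits are needed.

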Study endpoints:	
 
• Primary endpoint: 
 
○ To compare the ability of patients to forget their operated knee at 1 year after the surgery, measured by the Forgotten Joint Score 12 (FJS-12 Knee). The goal is to assess patient satisfaction regarding the surgery with a CE marked custom-made implant (ORIGIN®) versus off-the-shelf (VANGUARD PS) device with a self-administrated patient satisfaction questionnaire.
 
 
 
• Secondary endpoints: 
 
○ Evaluate the success of the procedure
 
○ Evaluate outcomes & complications & revision rate with the ORIGIN SYSTEM versus VANGUARD PS at the last (2y) follow-up visit
 
○ Evaluate performance of the ORIGIN System vs VANGUARD PS at 2 years follow-up: clinical examination and scoring. To evaluate/compare the clinical, functional and quality of life outcomes using the following scores: 
 
○ The Knee Injury and Osteoarthritis Outcome Score (KOOS)
 
○ The Oxford Knee Score (OKS)
 
○ The EQ-5D-5L Score
 
○ A self-administrated patient satisfaction questionnaire.
 
 
 
○ Evaluate the radiographic limb alignment, radiolucent lines and radiographic loosening (according to the “Modern Knee Society Radiographic Evaluation System and Methodology for Total Knee Arthroplasty” version 2015)
 
○ To evaluate/compare the radiological results (measurements and observations by surgeon reported scores: 
 
○ The Knee Society Score (KSS) (Objective Knee Indicators only)
 
○ Knee Society Radiographic Evaluation and Scoring System (KSRESS)
 
○ The Single Leg Stance Test (SLS)
 
○ The Timed Up & Go test (TUG)
 
 
 
 
 

N sites	1 – UMC MAINZ
Sample size	140  However, enrollment will occur at the time of the medical examination. It is assumed that the subjects’ treatments and follow-up visits will be performed per standard of care in the participating site
Total study duration:	48 months  
 
- Start- up phase: 3 months
 
- Enrolment: 18 months
 
- Follow-up phase: 24 months
 
- Study closure: 3 months
 

SYMBIOS		 symbios  Clinical Investigation Plan	F029.03

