### B. Evaluation of relevant clinical data (Registries, PMS, PMCFs)

As part of Symbios PMS, a prospective surveillance is established on the evaluated device. It includes the surveillance of all relevant scientific journals and regular electronic database (EMBASE, PubMed) review. A list of pertinent publications for this study is in the section XX. BIBLIOGRAPHY.

post-market surveillance also includes the current ongoing Symbios PMCF study CLIN-G-008: Evaluation of the performance and the safety of the ORIGIN® knee prosthesis and of the KNEE-PLAN® ORIGIN® instruments. (Study launched in 2018)

This study is related to 399 primary Total Knee Replacements, performed between 2018 and 2020. Indications are coherent with Instructions for Use. The mean follow-up is 1.0 year (max 1.6 year)

Preliminary results:

- Number of procedures                    399
- Gender                                        Females 52 % / Males 48 %
- Age     Mean 71.0 years
- Mean weight                                81.1 kg (33-177)
- Mean height                                168.7 cm (143-193)
- Mean Body Mass Index                28.4 (13-68)

Outcomes regarding performance:

- FJS score: compared to preoperative value, the Forgotten Joint Score is significantly improved at 3-6 months and at 1 year. According to the validated grading, the mean preoperative score (12.9/100) is poor and the mean score at 3-6 months (42/100) and at 1 year (60.5/100) is good
- Oxford Knee Score: compared to preoperative value, the Oxford Knee Score is significantly improved at 3-6 months and 1 year. According to the validated grading, the mean preoperative score (24.8/48) is poor and the mean score at 3-6 months (36.6/48) and at 1 year (41.2/48) is good
- ✓ Many of the patients are satisfied about their surgery (96% of satisfied or very satisfied)

At a mean follow-up of 1.0 year:

- ✓ The per-operative complication rate is 0.25%

[figure not shown]
SYMBIOS		 symbios  Clinical Investigation Plan	F029.03
Date	27.11.2019		Distribution Informatique pdf
Auteur	BGA		
Contrôle	EBO		
Libération	RAQ		

- ✓ The postoperative complication rate without revision is 3.25%
- ✓ The postoperative complication rate with revision is 0.25%

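### The sample size fits one zero-difference test of mean FJS-12, but the plan lists two primary items, scores the FJS inconsistently and leaves the role of 13.4 points open

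*Combined protocol and SAP*

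**What the plan says.** **Sizing (X.a, X.b).** Alpha is 0.05 with the two-sided normal quantile and power is 80%. The SD of the FJS is taken as 26.8 and the difference as half of that, 13.4 points. This gives at least 63 per group, raised to 70 for 10% loss. The null hypothesis appears only as a symbol in a generic table of error types. The normal distribution is cited for group size, not as the analysis. X.e defers all analyses to a SAP to be finished before analysis.

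**Primary endpoint (VI.B.a).** A singular primary endpoint is announced and two items follow: FJS-12 at 1 year, and "To compare patient satisfaction regarding the surgery with a CE marked custom-made implant" against the off-the-shelf device, using a short footnoted questionnaire. The synopsis puts both in one primary bullet ("device with a self-administrated patient satisfaction questionnaire"). The synopsis and VI.B.b also list the satisfaction questionnaire as secondary.

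**FJS scoring (VIII.F.e).** Twelve questions are scored 0 to 4, with zero best. "Low score means high satisfaction", and "All responses are summed and multiplied by 25 (Total= 0-100"). The same section closes by expecting ORIGIN to do better, "which should lead to a higher score (>13.4 points"). In IV.B a preoperative mean of 12.9 is graded poor, while "the mean score at 3-6 months (42/100) and at 1 year (60.5/100) is good".

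**Role of 13.4 points.** VI.C, X.a and X.b use it as an expected or planning difference. X.e has "Demonstrate superiority of ORIGIN over VANGUARD: higher score by 13.4 points based on MCID evaluation of PROMs".

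**Form of the variable (X.e).** The section also states that "patient satisfaction results will be analyzed into the knee awareness as" five ordered categories from never to mostly.

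**The concern.** A reader who follows the plan literally can reach different verdicts from the same data.

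- With two primary items and no rule, the trial could be declared positive on either one (error above 5%) or only on both (power below 80%).
- The scoring text gives the primary variable the wrong range and leaves its direction in dispute. Direction decides which arm a significant difference favours.
- If 13.4 points were taken as a success criterion, a result significant against zero could still be called a failure.

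The sizing covers none of these alternatives. The five-category wording adds a smaller doubt about whether a mean or a distribution of categories is analysed.

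**Working it through.** **1. Reproduce the plan's figure.** Inputs from X.a and X.b: SD 26.8, difference 13.4, ES = 13.4/26.8 = 0.5, quantiles 1.96 and 0.84.

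n = (2/0.5²) × (1.96 + 0.84)² = 8 × 7.84 = 62.72, so 63 per arm. Allowing for loss, 63/0.9 = 70. Both match. A one-sided test would need only 50, so the figure belongs to a two-sided test of zero difference on one endpoint, the FJS.

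**2. What that test does.** SE = 26.8 × √(2/n); power = Φ(13.4/SE − 1.96).

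| Per arm | SE | Significant from (1.96 × SE) | Power at true 13.4 |
|---|---|---|---|
| 63 | 4.775 | 9.36 | 80.1% |
| 70 | 4.530 | 8.88 | 84.1% |

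**3. Two primary items.** The test statistics are treated as bivariate normal, each tested two-sided at 5%. The plan gives neither a questionnaire effect size nor a correlation. I assume effect size 0.5 (needed only for the power columns) and correlations from 0 to 0.9.

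| Correlation | Either suffices: familywise error, neither item truly differs | Both required: power at 63 | Both required: power at 70 |
|---|---|---|---|
| 0 | 9.75% | 64.2% | 70.7% |
| 0.5 | 9.1% | 68.9% | 74.5% |
| 0.9 | 7.0% | 75.1% | 79.8% |

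At correlation 0 the error is 1 − 0.95² = 0.0975 and the joint power at 63 is 0.801² = 0.642. If the questionnaire has a real effect, rejecting its null is no error and only the 5% on the FJS remains.

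**4. FJS scoring.** Taken literally, the maximum is 12 × 4 × 25 = 1200. The mean item response × 25 has maximum 4 × 25 = 100, the stated range. The literal total is 12 times larger, so on that scale the planning values would be 12 × 13.4 = 160.8 and 12 × 26.8 = 321.6. The effect size is still 0.5, so the test of zero is unaffected, but 13.4 points would no longer mean what X.b intends.

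On direction, the low-is-best statement stands alone. The rise from 12.9 (poor) to 60.5 (good) in IV.B, the superiority line in X.e and the closing sentence of VIII.F.e all take higher as better.

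**5. If 13.4 were a success criterion.** At a true difference of 13.4:

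- Observed difference must reach 13.4: power = Φ(0) = 50% at any n. At 63 per arm, 80.1% − 50% = 30.1% of trials would be significant against zero yet miss 13.4. Under no true difference the chance of reaching 13.4 is 1 − Φ(13.4/4.775) = 1 − Φ(2.806) = 0.25%, so type I error is not inflated.
- Lower 95% limit must exceed 13.4: power = Φ(−1.96) = 2.5% at any n.

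**The case against.** The strongest reply is that the intended test can be recovered and that details belong in the SAP. Much of this stands. The sizing implies one rule, its arithmetic is right, and X.e sends the analyses to a SAP that is listed as a separate document. A reader might infer from the undefined null hypothesis that the trial has no primary test, or that it is undersized. The documents support neither; an unnamed test alone is missing detail.

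A reader might also infer that 13.4 points is a pass mark. That is the weaker reading. The X.e line sits in a list of places where differences might be found, next to baseline demographics and modular stems. VIII.F.e voices an expectation, and VI.C, X.a and X.b use 13.4 for planning. Still, no section rules the stricter reading out.

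On the two items, VI.B.a uses the singular and X.d says patient satisfaction is assessed through the FJS. But VI.B.a footnotes a separate instrument, and the schedule of assessments collects the two separately, so they cannot be merged.

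On scoring, the zero-is-best remark may describe single item responses, and the multiplier looks like a drafting slip. That makes a reversed conclusion unlikely, but the text still needs correcting.

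Finally, the unblinded design and the sponsor's eCRF check might suggest that the rule could be fitted to the data. Section XI.c describes a completeness check and requires evaluability decisions before database lock, so the documents do not show this.

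**Conclusion.** The plan is wrong as written on two counts and ambiguous on a third.

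1. **Primary endpoint.** Two items are listed and only the FJS is sized. The cost is a familywise error of 7.0% to 9.75% if either suffices and neither truly differs, or power of about 64% to 75% at 63 per arm if both are required. The range reflects assumed correlations of 0.9 to 0; the power figures also assume a questionnaire effect size of 0.5.
2. **FJS definition.** The formula does not give the stated range, and the stated direction conflicts with the plan's own use of the score. This follows from the text and needs no assumption.
3. **13.4 points.** Probably the planning difference, but not labelled as such. The 50% and 2.5% figures apply only if a success criterion was meant.

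The sample size stands for a single zero-difference test of mean FJS. Two nearby wordings are minor clarifications: V.A expects improvement whichever implant is received, and the close of VI.B judges endpoints on change from before surgery to 2 years. The formal hypothesis in VI.C does compare arms.

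**What to change.** - **Synopsis, VI.B.a and X.e:** name the between-arm difference in mean FJS-12 at 1 year, tested two-sided at 5% against zero and reported with its 95% CI, as the sole primary analysis.
- **Questionnaire:** make it secondary, or test it at 5% only after FJS-12 is significant, which keeps the overall error at 5%.
- **VIII.F.e:** define the score as mean item response × 25, reversed so that higher is better (100 − 25 × mean item response, range 0 to 100), and remove the low-is-best statement.
- **VIII.F.e and X.e:** label 13.4 FJS points as the planning difference and an aid to interpretation, not a pass mark.
- **X.e:** state that the never-to-mostly categories are descriptive.
- **SAP:** sign it before database lock and before any comparative outcome summary by arm is produced. Barring everyone from seeing outcomes by arm would not work, because the study is unblinded and investigators sign every CRF.
- **V.A and the close of VI.B:** align with VI.C.

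**Cost.** A protocol amendment with ethics committee approval and co-investigator signatures (XIII, XIV), and matching SAP text. The questionnaire loses equal primary status; in fixed order its chance of success is the joint power above, about 64% to 75% at 63 per arm under the same assumptions. Sample size and data collection do not change.
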